In addition to reaching out to Veterans on the high-risk list, we also will engage Veterans via the New Haven VA psychiatric Emergency Room, inpatient units, and individual New Haven clinicians. Specifically, we will engage with staff to find out if any Veteran has received a score on the Columbia-Suicide Severity Rating Scale Screen of 3 or greater in the last three months. This measure is used commonly in the VA. Such a score is known to be an optimal cut off score for identifying individuals who would likely attempt suicide. In a recent study of nearly 19000 patients, those scoring over the cut-off of ≥ 3 had almost four times the odds of dying by suicide within 1 week and 1 month, respectively, and doubled the odds of dying within a year⁹⁰. We will also engage with individual clinicians to assess whether any of their patients have recently received a score of ≥ 3 on the Columbia measures. In addition, we will ask these staff about any Veteran who made a suicide attempt in the last three months. Thus, the additional recruitment criteria we are adding will be:

- Any Veteran from the New Haven VA psychiatric Emergency Room, the New Haven inpatient units, or from individual New Haven clinicians who received a score on the Columbia-Suicide Severity Rating Scale Screen of 3 or greater in the last three months
- Any Veteran from the New Haven VA psychiatric Emergency Room, the New Haven inpatient units, or from individual New Haven clinicians who made a suicide attempt within the last three months

Each month, there are approximately 105 VHA patients with PRFs for suicide risk at the CT VA campuses. In addition to those Veterans with a PRF, we also will be recruiting those Veterans with suicidal ideation or attempts. This pool of Veterans should be sufficient to recruit participants for the pre-pilot (n=12) and formal pilot (n=12). Assuming a 75% retention rate (as achieved in [name] PREVAIL pilot)¹⁵ this will yield a final sample of 18 patients with outcome data at post-intervention and 3-month follow-up. This sample size will yield reasonably precise estimates of feasibility in terms of actual rates of recruitment, retention, compliance/fidelity to intervention, and completion of outcome assessments.

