5.5 Study Evaluations

Measures

The measures used to collect data for Aims 1 and 2 include data from the CPRS record as well as several rehabilitation and depression & suicide variables described in further detail below. Additionally, a study-specific form will be used to collect information about age, sex, race, ethnicity, employment, education, income, and marital status.

Rehabilitation Variables

Sheehan Disability Scale (SDS)⁶⁴. The SDS uses 3 items to measure how much work, social life, and family life are impaired by mental health symptoms. The SDS has been widely used in diverse samples,⁶⁵⁻⁶⁷ including Veterans,^{68,69} and found to be psychometrically sound and sensitive to treatment effects.

Temple University Community Participation scale (TUCP)⁷¹. The TUCP is a 26-item measure of community inclusion in the past month. The TUCP has been used in previous studies with good reliability.⁷¹⁻⁷⁴

Questionnaire about the Process of Recovery (QPR)⁷⁵. The QPR contains 15 items that measure connectedness, hope, identity, meaning, and empowerment. The QPR has demonstrated high internal and convergent validity as well as sensitivity to change.^{76,77}

Quality of Life Enjoyment and Satisfaction Questionnaire (Q-LES-Q-SF). The Q-LES-Q-SF consists of 16 items to assess life satisfaction in the past week. The Q-LES-Q-SF has been used extensively with Veterans as part of the National Health and Resilience in Veterans Study (NHRVS).

Depression and Suicide Variables

Quick Inventory of Depressive Symptoms (QIDS)⁷⁹. The QIDS consists of 16 questions to assess depression severity. The QIDS has demonstrated high reliability, validity, and sensitivity to treatment change,⁸⁰, including among Veterans.⁸¹

Columbia-Suicide Severity Rating Scale (C-SSRS)⁸². The C-SSRS is used to assess suicidal ideation (past 30 days) and behaviors (past 3 months). Suicide ideation items include: (1) wish to be dead, (2) non-specific suicidal thoughts, (3) suicidal thoughts with methods, (4) suicidal intent, and (5) suicidal intent with plan. The suicide behavior subscales include: (1) attempts (actual, aborted, interrupted), (2) preparatory behavior, and (3) non-suicidal self-injurious behavior. We will also use two measures of psychosocial variables that potentially mediate suicide risk and are hypothesized to be impacted by PSs.

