## Statistical Analysis Plan

Grant Title: Peer Based Suicide Prevention

ClinicalTrials.gov ID: NCT04222673

Sponsor: VA Office of Research and Development

Document date: March 8, 2022

Given the small sample size and recommendations for pilot studies, quantitative analyses were descriptive (e.g., frequencies, means) and based on the Reliable Change Index (RCI) for each participant for each outcome measure. The RCI is used to determine whether pre- to post-score differences are statistically reliable and to categorize changes as either improved, deteriorated, or indeterminate. A statistical threshold of RCI score  $z = \pm 1.96$  and  $p < .05$  was used to establish clinical significance.

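### Read as covering the C-SSRS, the SAP's reliable-change rule can label a repeat suicide attempt indeterminate and cannot register worsening from the top of the ideation items

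*SAP*

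**What the plan says.** The SAP bases its quantitative analysis on descriptive statistics and on the RCI "for each participant for each outcome measure". It explains the index as follows: "The RCI is used to determine whether pre- to post-score differences are statistically reliable", and the result is used "to categorize changes as either improved, deteriorated, or indeterminate". The threshold is z = ±1.96 with p < .05. No measure is named or excluded, no SD or reliability is given, and no separate rule covers a suicide attempt.

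Protocol section 5.5 lists the C-SSRS among the depression and suicide variables: "The C-SSRS is used to assess suicidal ideation (past 30 days) and behaviors (past 3 months"). The ideation items are "1) wish to be dead, (2) non-specific suicidal thoughts, (3) suicidal thoughts with methods, (4) suicidal intent, and (5) suicidal intent with plan". Behaviours are kept apart from ideation: "The suicide behavior subscales include: (1) attempts (actual, aborted, interrupted), (2) preparatory behavior, and (3) non-suicidal self-injurious behavior". Section 5.5 gives no scoring rule for either part. Section 3.0 makes suicide-related outcomes part of Aim 2.

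On entry, section 5.2 recruits from the list of active Patient Record Flags, which can be set for a recent attempt. It adds Veterans who "received a score on the Columbia-Suicide Severity Rating Scale Screen of 3 or greater in the last three months", and Veterans with an attempt in that same period.

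**The concern.** The RCI compares two measurements of a quantity that can move in either direction. Two parts of the C-SSRS do not behave like that.

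Behaviours are events within a look-back window. Recruitment favours people who may already have an attempt in the baseline window, so a further attempt during the intervention need not change the score.

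Ideation is a short, bounded set of ordered items, and the study recruits a high-risk group. A person who starts near the top has little or no room to rise, yet plenty of room to fall.

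At stake is how the response categories are read. A count of deteriorated participants that leaves out a repeat attempter, or someone already at the maximum, would look more reassuring than the data behind it. The study expects 24 × 0.75 = 18 Veterans with outcome data, so one such person is 1/18 = 5.6% of the group.

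**Working it through.** **The plan's own figure.** The two-sided 5% normal critical value is 1.95996, and the two-sided p-value at 1.96 is 0.049996. The SAP's z and p agree.

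**Formula.** RCI = (post − pre) / [SD × √(2(1 − r))], where r is reliability. The smallest change that can be classified is therefore 1.96 × SD × √(2(1 − r)).

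**Inputs.** From the documents: the threshold and three categories (SAP); the five ideation items and the two look-back windows (protocol 5.5); the recruitment routes (protocol 5.2). Assumed, because the documents are silent: ideation scored 0-5 by the highest item endorsed; behaviour scored 0/1 for any attempt; the SDs and reliabilities below.

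**Behaviour, any-attempt score.**
- Attempt before baseline and another during PREVAIL: 1 − 1 = 0, so RCI = 0 and the label is indeterminate, whatever the SD and reliability.
- No attempt before baseline, one during PREVAIL: 1 − 0 = 1. With SD = √(p(1 − p)), prevalence p from 0.1 to 0.5 and r from 0.5 to 0.9, the threshold runs from 0.26 to 0.98. A change of 1 exceeds all of these, so the label is deteriorated.
- Scoring the number of attempts would not remove the problem. One before and one during is still zero change, and two before and one during is a fall of 1.

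**Ideation, 0-5 score.** Threshold in points, with the smallest whole-point rise that reaches it:

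| SD | r = 0.7 | r = 0.8 | r = 0.9 |
|---|---|---|---|
| 1.0 | 1.52 (2) | 1.24 (2) | 0.88 (1) |
| 1.25 | 1.90 (2) | 1.55 (2) | 1.10 (2) |
| 1.5 | 2.28 (3) | 1.86 (2) | 1.31 (2) |

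Room to rise is 5 − baseline:
- From 5 the room is 0, so deteriorated is unreachable in 9 of 9 combinations.
- From 4 the room is 1, so it is unreachable in 8 of 9.
- From 3 the room is 2, so it is unreachable in 1 of 9.

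The largest change needed is 3 points, so improved is reachable from 4 and from 5 in all nine.

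**Wider range.** With SD from 0.8 to 2.0 and r from 0.5 to 0.95 (36 combinations), deteriorated is reachable in 0 of 36 from baseline 5, 7 of 36 from 4, 23 of 36 from 3, 31 of 36 from 2, and 36 of 36 from 0 or 1.

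**Example, SD 1.5 and r = 0.8.** The denominator is 1.5 × √0.4 = 0.949 and the threshold is 1.86. A change from 5 to 3 gives −2/0.949 = −2.11, improved. A change from 4 to 5 gives 1/0.949 = 1.05, indeterminate.

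**The case against.** The SAP never names the C-SSRS, and the protocol defines neither a 0-5 total nor a behaviour score. That stands: the examples depend on assumed scoring. It does not dispose of the point, because the SAP's scope has no exclusion and a reader following it would have to choose a score and apply the rule.

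A reader might infer that the RCI categories are the pilot's only view of worsening suicidality. The documents do not support this. The protocol abstract plans chart review for visits involving suicidal behaviour, section 5.6 plans descriptive statistics for each measure at each assessment, and section 6.0 requires adverse event monitoring and reporting. Nor do the criteria for moving to a larger trial use a deterioration count; they are enrolment above 50% and follow-up completion above 70%. The absence of a Data Monitoring Committee adds nothing here, since section 5.1 manages acute risk as it arises and the RCI is a label applied afterwards.

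A reader might also infer that a behaviour score would mix suicidal events with non-suicidal self-injury. The protocol lists that as a separate subscale and states no composite.

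RCI labels apply to a measure, not to a person. Someone who attempts suicide and is labelled improved on past-30-day ideation may be described correctly on ideation. That is fair, and the point does not rest on that case.

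On the ceiling, worsening is strictly unrecordable only at the maximum. The Screen score used for recruitment covers three months and does not fix the past-30-day baseline score, and the Aim 2 inclusion list in section 5.4 names only the Patient Record Flag. The asymmetry also reverses at the bottom of the scale, where improved becomes hard or impossible to reach.

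Finally, the scales kept under the RCI are bounded too. Their ceilings could not be checked, because no SDs or reliabilities are given.

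**Conclusion.** The concern holds in a limited form. If the RCI is applied to the C-SSRS, as the SAP's wording implies, it gives a misleading category in two situations. A repeat attempter is indeterminate on an any-attempt score whatever the SD and reliability. A Veteran at the top of a 0-5 ideation score can never be deteriorated, and one at 4 cannot be in 8 of 9 combinations over SD 1.0 to 1.5 and reliability 0.7 to 0.9 (29 of 36 over the wider range).

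It would go too far to say that the plan misses suicide attempts, that any attempter would escape the deteriorated label, or that most participants will start at the ceiling. Other data sources record attempts, a first attempt after baseline would be labelled deteriorated on an any-attempt score, and the documents give no baseline ideation distribution. The defect lies in the category, not in data capture.

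**What to change.** Amend the SAP in three places:

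1. Limit the RCI to the multi-item scales: SDS, TUCP, QPR, Q-LES-Q-SF, QIDS, INQ and SCS.
2. For C-SSRS behaviours, report the number of Veterans with any actual, interrupted or aborted attempt, or preparatory behaviour, after baseline. Count each such Veteran as worsened whatever the change on any scale.
3. For C-SSRS ideation, state the score used and show a baseline-by-post shift table, with the number of Veterans who started at 4 or 5.

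The cost is a few lines of SAP text and two small descriptive tables from data the study already collects. No visit, assessment or clinical procedure changes. The drawback is that the C-SSRS would no longer carry an RCI category alongside the other scales.

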5.4 Inclusion/Exclusion Criteria

Inclusion Criteria for Aim 1 Veterans

1. Experience related to suicide
2. Voluntary informed consent (must be able to be given by the patient)
3. Age 18 and older
4. Fluent in English

Exclusion Criteria for Aim 1 Veterans

1. Active suicidal flag or currently hospitalized
2. Pregnant and/or incarcerated
3. Unable to provide voluntary, written informed consent for any reason (include incompetency)

Inclusion Criteria for Aim 1 Staff

1. Voluntary informed consent
2. Age 18 and older

3. Peer Specialists with experience related to suicide (Peer Specialists only)
4. Staff members with experience related to treating Veterans with experience related to suicide (Staff members only)
5. Fluent in English

Exclusion Criteria for Aim 1 Staff

1. Unable to provide voluntary, written informed consent for any reason

Inclusion Criteria for Aim 2 Veterans

1. Voluntary informed consent (must be able to be given by the patient) or voluntary informed assent with consent of a conservator if applicable
2. Age 18 and older
3. High suicide risk evidenced by a Patient Record Flag in their medical chart.
4. Fluent in English

Exclusion Criteria for Aim 2 Veterans

1. Substantially cognitively impaired as indicated by a score of 10 or higher on the Blessed Orientation, Memory, Concentration (BOMC) Test
2. Unable to provide voluntary, written informed consent for any reason (include incompetency)
3. Determined by patient's attending psychiatrist that the peer-based intervention is not appropriate due to unstable psychosis, cognitive disorder, or severe personality disorder
4. Residing outside of the VA Connecticut catchment area
5. Pregnant and/or incarcerated

Inclusion Criteria for Aim 2 Peer Specialists

1. Voluntary informed consent
2. Age 18 and older
3. Employed by the VA as a Certified Peer Specialist

Exclusion Criteria for Aim 2 Peer Specialists

1. Unable to provide voluntary, verbal consent for any reason

2. Determined by Peer Specialists' supervisor, attending psychiatrist, or other clinician that delivering the intervention is not appropriate due to prior trauma, clinical instability, or current concerns with suicide risk

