5.6 Data Analysis

Per SPiRE protocol and discussions with an RR&D Scientific Program Manager, calculations for power and estimated effect size are not required because our proposal involves piloting a rehabilitation intervention with a small, high risk sample of VHA patients (as opposed to determining effectiveness in large samples via inferential statistical hypothesis testing).

Aim 1

Qualitative analyses of interviews from the needs assessment will be conducted with empirical phenomenological procedures used successfully by our team in previous studies.⁵⁷ Verbatim transcripts of audio recordings from the interviews will be distributed to the Co-Investigators. Each researcher will independently review, analyze, and code the transcripts for themes that characterize participants' experiences. After creating a narrative summary using the participants' own language, they will review each of their summaries to compare/contrast the identified themes before coming to consensus about important themes. A synthesized report will summarize the overarching themes.

Aim 2

WOC employees from the Program for Recovery and Community Health (PRCH) will conduct the data analysis for this aim. In line with SPIRE guidelines and recommendations for pilot studies,^{28,89} our focus will be on the feasibility of the intervention and assessment of outcomes. Therefore, quantitative analysis will be mostly descriptive in nature (e.g., frequencies, percentages, means, standard deviations) and will focus on the estimation of confidence intervals. This includes descriptive statistics on each of the measures at each assessment period, creation of confidence-intervals, and visual plotting of data to observe potential trends in the data associated with the intervention. Formal hypothesis testing will not be conducted as comparisons of outcomes would be unreliable estimates of any true effect given the small sample size. Instead, analyses will be used to evaluate the feasibility of measuring the primary outcomes and potential mediators as well as to inform decisions about power and sample sizes in a larger trial. Qualitative analyses of post-intervention interviews with Veterans will follow the same procedures as described for Aim #1. Qualitative analysis of interviews and/or focus groups with Peers Specialists conducted after completing the PREVAIL training and the pre-pilot of the intervention will also follow the same procedures as described in Aim #1.

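### The SAP treats an RCI threshold of z = ±1.96 as proof of clinical significance, but the RCI as the SAP defines it shows only that a change is statistically reliable

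*SAP*

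**What the plan says.** The Statistical Analysis Plan is a single paragraph. It bases the participant-level analysis on the RCI, computed "for each participant for each outcome measure". It then defines the index: "The RCI is used to determine whether pre- to post-score differences are statistically reliable". The same sentence gives its second use, "to categorize changes as either improved, deteriorated, or indeterminate". The final sentence sets the threshold at z = ±1.96 with p < .05, calls it statistical, and says that it "was used to establish clinical significance".

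Protocol section 5.6 (Data Analysis, Aim 2) does not mention the RCI or clinical significance. It says that "quantitative analysis will be mostly descriptive in nature" and lists "descriptive statistics on each of the measures at each assessment period, creation of confidence-intervals, and visual plotting of data".

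**The concern.** Two adjacent SAP sentences give one threshold two different meanings. The first is that the change is larger than measurement error would readily produce. The second is that the change matters clinically. Meeting the first does not establish the second.

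A report that follows the SAP could describe participants as clinically significantly improved or deteriorated when only measurement error had been ruled out. It could also imply that a large change on a less reliable instrument was not clinically significant, when the only finding was that measurement error could not be excluded. The RCI is the only participant-level outcome rule in the SAP, and section 2.0 of the protocol says the data will inform a proposal for a multi-site randomized trial. The label is therefore likely to be carried forward.

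**Working it through.** **1. The plan's own figure.** The two-sided 5% normal point is 1.95996, and 2 × (1 − Φ(1.96)) = 0.0500. The one-sided value is 0.0250. So z = ±1.96 and p < .05 agree as a two-sided criterion. The number is right; the question is what it can establish.

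**2. Is there a clinical criterion elsewhere?**

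- Protocol 5.5 describes the SDS, TUCP, QPR, Q-LES-Q-SF, QIDS, C-SSRS, INQ and SCS by content and general psychometric statements. It gives no important difference, normative range, or response or remission rule.
- Protocol 5.6 has none.
- Two instrument cut-offs appear, and both concern entry. Section 5.2 recruits Veterans "who received a score on the Columbia-Suicide Severity Rating Scale Screen of 3 or greater in the last three months". Section 5.4 excludes those "Substantially cognitively impaired as indicated by a score of 10 or higher on the Blessed Orientation, Memory, Concentration (BOMC) Test".
- The Abstract's thresholds (> 50% enrollment, > 70% follow-up) concern feasibility and acceptability, not scores.
- The Data Safety and Monitoring plan in section 5.1 ties certain QIDS or C-SSRS responses to a hand-off to a licensed clinician. These are safety triggers, not score cut-offs or criteria for change.

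The three RCI categories do not fill the gap. They give the direction of a reliable change, or say that reliability was not shown.

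**3. What the threshold responds to (illustration).** The SAP writes out no formula, SD or reliability. Assume the standard form:

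RCI = d / (SD × √(2(1 − r)))

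where d is the change and r the reliability. The smallest change that reaches 1.96, in SD units, is 1.96 × √(2(1 − r)).

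| Assumed r | Smallest flagged change (SD) | RCI for a 1.0 SD change |
|---|---|---|
| 0.95 | 0.62 | 3.16 |
| 0.90 | 0.88 | 2.24 |
| 0.85 | 1.07 | 1.83 |
| 0.80 | 1.24 | 1.58 |
| 0.70 | 1.52 | 1.29 |

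- Ratio of bars: 1.240 / 0.620 = 2.0 for r from 0.80 to 0.95, and 1.518 / 0.620 = 2.4 for r from 0.70 to 0.95.
- A 1.0 SD change passes at r = 0.90 and fails at r = 0.80.
- The label switches at r = 1 − (d/1.96)²/2, with d in SD units: 0.93 for 0.75 SD, 0.87 for 1.0 SD and 0.80 for 1.25 SD.

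No clinical quantity enters any of these expressions.

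**4. Flags from error alone (illustration).** Section 5.2 expects 24 × 0.75 = 18 participants with outcome data. With no true change and normal errors, each measure would flag 18 × 0.05 = 0.9 participants on average. The chance of at least one flag per measure is 1 − 0.95¹⁸ = 0.60. Under the SAP's wording these would count as clinically significant changes.

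**The case against.** The strongest reply is that this is one loose phrase in a paragraph that discloses the rule. The SAP calls the threshold statistical, gives z and p, and none of its three categories is named clinically significant. Progression rests on enrollment and follow-up rates, and formal hypothesis testing is ruled out, so no trial decision turns on the phrase. That is a fair account of its reach and limits the weight of the point. It does not remove the error, because the sentence states what the threshold was used to establish, and a report that follows it would overclaim.

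A second reply is that a cut-off varying with reliability is a property of any RCI and would be the same after renaming. That is true, and the illustration shows no misclassified participant. Such variation is proper for a measure of reliable change. It is a fault only when the same cut-off is presented as a clinical standard.

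A third reply is that withholding a label while measurement error remains possible is what an RCI is for, and that adding a clinical criterion on top of the RCI would still withhold it. With no criterion pre-stated, however, the remedy is to drop the term altogether, so no large change is selectively denied it.

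Finally, the sources the SAP cites for the RCI were not available and may use the term differently. The point is therefore confined to the SAP's own definition and wording.

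**Conclusion.** The concern holds and should be fixed. By the SAP's own definition the rule can show change beyond measurement error, and neither document contains anything that would turn that into clinical significance. This conclusion comes from reading the text and needs no assumed figure.

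The sizes are illustrative. They rest on the standard RCI formula and assumed reliabilities: a two-fold difference in the bar between r = 0.80 and r = 0.95, and for a 1.0 SD change a switch of label at r = 0.87. The false-flag figures also assume normal errors and 18 completers.

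The effect is limited to how outcomes are described. The Abstract's feasibility and acceptability criteria, the suicide risk protocol in section 5.1, adverse event reporting in section 6.0, and the descriptive statistics, confidence intervals and plots in section 5.6 do not use the RCI.

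**What to change.** In the SAP and in every report, state that the threshold serves *to classify reliable change (change beyond measurement error)* and remove the claim about clinical significance. Use *clinically significant* only for a participant who also meets a clinical cut-off or important difference stated in advance for that instrument. If none was stated in advance, drop the term. It would help readers, though the correction does not depend on it, to list the SD and reliability behind each RCI so that the size of change each label represents is visible.

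The correction costs one phrase and one sentence, with no new data or analysis; the optional list would be a small table covering eight instruments. The downside is that fewer participants, or none, can be described as clinically significantly changed.
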